2.3 POTENTIAL RISKS AND BENEFITS

2.3.1 KNOWN POTENTIAL RISKS

Collected human plasma may be used as a therapeutic product (known as “plasma” or “fresh frozen plasma”) or as source material for the production of pharmaceutical fractionated products (known as “plasma products” or “plasma derivatives”) ([Burnouf 2007](#)). GRF6019, a [REDACTED] human plasma protein fraction, [REDACTED] serves as a viable source of soluble, infusible plasma proteins from [REDACTED] healthy donors.

[REDACTED]

ABO antigen typing is not required prior to administration. Finally, the additional steps taken during production to remove viral pathogens provide an increased margin of pathogen safety in comparison to fresh frozen plasma.

[REDACTED] GRF6019 is not expected to significantly alter the urinalyses of recipients, their bleeding times, coagulation times, prothrombin times, prothrombin consumption, platelet counts or fibrinogen levels when given in quantities of up to 1000 mL. Hypotension may occur, particularly following rapid infusion or intraarterial administration to patients on cardiopulmonary bypass. The blood pressure may normalize spontaneously after the slowing or discontinuation of the infusion. [REDACTED]

[REDACTED]

GRF6019 is made from human plasma and may carry a risk of transmitting infectious agents, e.g., viruses, the variant Creutzfeldt-Jakob disease (vCJD) agent, and, theoretically, the Creutzfeldt-Jakob disease (CJD) agent. The risk that GRF6019 can transmit an infectious agent has been reduced by screening plasma donors for prior exposure, testing donated plasma, and including manufacturing steps with the capacity to inactivate and/or remove pathogens.

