4.1 Description of the Study Design, 5.4.2 Handling of Participant Withdrawals or Termination, 7.3.7 Early Termination	Updated language to clarify that subjects who have received at least one dose of GRF6019 but withdraw/terminate from the study early may be invited to complete the end of study procedures.	To clarify that end of study procedures do not need to be completed for subjects who terminate from the study prior to initial dosing (e.g. Visit 3).
5.1 Inclusion Criteria, 7.1.1.1.11 Echocardiogram	Removed the upper limit for systolic ejection fraction. Subjects will be eligible for inclusion if they have a systolic ejection fraction that is greater than or equal to 55% and no other clinically significant abnormalities are noted.	Unless there is evidence of cardiac pathology on echocardiography, an elevated ejection fraction is not a safety concern. Echocardiography will be used at screening to exclude subjects with an ejection fraction of less than 55% and subjects with other echocardiographic abnormalities, including impaired diastolic function (e.g. impaired diastolic relaxation) or hypertrophic cardiomyopathy.
5.2 Exclusion Criteria	
Previously read:
 
 Heart disease (or history thereof), as evidenced by myocardial infarction, unstable, new onset or severe angina, or congestive heart failure (New York Association Class II, III or IV) in the 6 months prior to dosing; uncontrolled high blood pressure (systolic blood pressure of 160 mmHg or higher and/or diastolic blood pressure of 100 mmHg or higher) despite treatment during the 3 months prior to 	
Protocol clarity and standardization.
 
Addition of exclusion criterion for subjects with treatment-refractory hypertension because such subjects may be more likely to experience a hypertension during GRF6019 infusions.

Location	Description	Purpose
	
dosing.
 
Now reads:
 
 Heart disease, including myocardial infarction, unstable, new onset or severe angina, or congestive heart failure (New York Association Class II, III or IV) in the 6 months prior to dosing; Poorly controlled high blood pressure (systolic blood pressure of 160 mmHg or higher and/or diastolic blood pressure of 100 mmHg or higher) despite treatment during the 3 months prior to dosing, or treatment refractory high blood pressure, defined as treatment requiring 3 or more antihypertensives from different classes. 	

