6.3 Vital Signs

Summary statistics will be presented for the actual values and change from baseline values (as appropriate) at each time point for all vital signs (Temperature, Pulse Rate, Systolic Blood Pressure (BP), Diastolic BP, Respiratory Rate) and weight. Changes from baseline for all vital sign parameters and weight will include pre-dose at Day 1 to pre-dose at subsequent days and at all timepoints during infusion (Table 14.3.3.1). In addition, changes from baseline for all vital sign parameters will include pre-dose at each infusion day to all post-dose timepoints within each infusion day (Table 14.3.3.2).

The incidence of the following categorized blood pressure values and changes from baseline will be summarized (Table 14.3.3.3):

- Systolic BP > 180
- Systolic BP > 200
- Systolic BP < 90
- Diastolic BP > 110
- Diastolic BP > 120
- Diastolic BP < 50
- An absolute change of >30% from Day 1 pre-dose (baseline) in systolic and/or diastolic BP. This change includes positive and negative percent changes.

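### SAP 6.3: the only relative-change count of measured blood pressure pools rises with falls and systolic with diastolic, so the row cannot show the direction of a dose difference

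*SAP*

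**What the plan says.** Table 14.3.3.3, defined in SAP 6.3, has seven rows. Six are absolute limits, and each is specific to one parameter and one direction: systolic above 180, above 200 and below 90; diastolic above 110, above 120 and below 50. The two low rows read "Systolic BP < 90" and "Diastolic BP < 50". The seventh is the only row based on change: "An absolute change of >30% from Day 1 pre-dose (baseline) in systolic and/or diastolic BP. This change includes positive and negative percent changes". Under SAP 2.6 the table is shown by dose group and overall.

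Three other places bear on the point:

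- SAP 6.3 also summarises signed change for each vital sign separately, from the Day 1 pre-dose value (Table 14.3.3.1) and from each infusion day's own pre-dose value (Table 14.3.3.2).
- SAP 6.1.5 tabulates blood-pressure adverse events by preferred term and dose group (Tables 14.3.1.7.1 to 14.3.1.7.3). The example terms separate increases from decreases and systolic from diastolic.
- SAP 8 explains that which blood-pressure values counted as adverse events of special interest was left to the investigator, and that the ranges in 6.3 were set for that reason.

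**The concern.** The protocol raises concerns in both directions. Section 2.3.1 warns: "Hypotension may occur, particularly following rapid infusion". The treatment-refractory hypertension exclusion, which still stands in section 5.2, is justified in the revision history "because such subjects may be more likely to experience a hypertension during GRF6019 infusions". The Protocol Summary gives both doses the same 2 to 3 hour infusion, so the 250 mL group receives 2.5 times the volume in the same window. Whether blood pressure moves up or down, and at which dose, is therefore a real question for a trial whose primary objective is safety.

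One row that accepts a move either way in either parameter cannot answer it. Two groups with the same printed count may differ in kind, and background movement in one direction waters down a dose-related excess in the other.

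**Working it through.** The documents give no expected rate, standard deviation or power for this row, so there is no stated figure to reproduce. The check has four steps.

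**1. Which outputs separate direction?**

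| Output | Direction separated? | Counts large relative changes in measured values? |
|---|---|---|
| Table 14.3.3.3, six limit rows | Yes | No, absolute limits only |
| Table 14.3.3.3, >30% row | No | Yes |
| Tables 14.3.3.1 and 14.3.3.2 | Yes (signed) | No: n, mean, median, min, max, SD (SAP 2.6) |
| Tables 14.3.1.7.1 to 14.3.1.7.3 | Yes, by preferred term | No, reported adverse events |

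No output does both.

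**2. When does a change just over 30% also reach a directional row?** Set the changed value equal to the nearest limit and solve for baseline:

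- Systolic fall: 0.70 × baseline = 90, so baseline = 128.6. A just-over-30% fall from a higher baseline stays at or above 90.
- Diastolic fall: 0.70 × baseline = 50, so baseline = 71.4.
- Systolic rise: 1.30 × baseline = 180, so baseline = 138.5. A just-over-30% rise from a lower baseline does not exceed 180.
- Diastolic rise: 1.30 × baseline = 110, so baseline = 84.6.

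For example, systolic 150 falling to just under 105 (0.70 × 150), or diastolic 80 falling to just under 56 (0.70 × 80), appears among measured values only in the pooled row. For systolic baselines between 128.6 and 138.5, and diastolic baselines between 71.4 and 84.6, just-over-30% changes in both directions appear only there. From diastolic 80 the two values are 56 and 104.

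**3. How much does pooling dilute?** There are 20 subjects per group (SAP 1.3). Assume falls in 5% v 30% (100 mL v 250 mL), with falls and rises independent, so pooled rate = 1 − (1 − fall)(1 − rise). The last column is two-sided Fisher power at 0.05. It only measures signal loss, since SAP 6.3 specifies no test for this row.

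| Assumed rises (100 v 250 mL) | Pooled row | Difference | Power |
|---|---|---|---|
| none (equals a fall-only row) | 5% v 30% | 25 points | 0.45 |
| 10% v 10% | 14.5% v 37% | 22.5 points | 0.26 |
| 20% v 20% | 24% v 44% | 20 points | 0.18 |
| 20% v 10% | 24% v 37% | 13 points | 0.09 |
| 30% v 5% | 33.5% v 33.5% | 0 | – |

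The third line in full: 1 − 0.95 × 0.80 = 0.24 and 1 − 0.70 × 0.80 = 0.44.

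**4. Background from ordinary variation.** This was simulated for diastolic pressure with no drug effect. Assumed: 20,000 subjects, mean 75 mmHg, one Day 1 reading, 10 infusion days with 5 readings each, and within-subject SD s split into a day part of 0.7s and a reading part of 0.714s. At s = 7, 10.9% have a fall over 30%, 21.9% a rise, and 32.8% either. At s = 9 the figures are 33.9%, 39.6% and 70.6%. At s = 5 the pooled figure is only about 5%. The result depends on an SD and a number of readings that the documents do not give.

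**The case against.** The strongest reply is that the row is one deliberately broad screen beside finer outputs. A reading below 90 systolic or 50 diastolic is counted as a low reading in the same table. Hypotension and hypertension have separate preferred terms by dose, divided into events during and after infusion. Signed changes for systolic and diastolic would tend to show opposite shifts with opposite signs, and Listing 16.2.9 carries the vital-sign data. The row also follows the form of the protocol's criterion in section 8.4.3, which has a 25% cut-off, states no direction and joins the two parameters. SAP 8 declares the revised ranges. The output is descriptive, with 20 subjects per group.

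Most of this stands. A reader might infer that hypotension is merged with hypertension throughout the blood-pressure analysis; the outputs just listed show that it is not. A reader might also infer that a dose effect would cancel out. That needs opposite dose gradients of similar size, for example falls in 1 v 6 subjects and rises in 6 v 1 other subjects, printing as 7 v 7. Nothing in the documents suggests such a pattern. With equal background rises the row is diluted and does not cancel.

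The reply does not close the gap in step 2. The adverse-event tables depend on an event being reported, and SAP 8 introduces the measured ranges because the classification of blood-pressure values was discretionary. The continuous summaries show averages and extremes at each timepoint but no number of subjects. The criterion in section 8.4.3 is a reporting trigger, whereas this table compares doses, so sharing its form is a weak reason to pool.

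**Conclusion.** The point holds for one row. The only relative-change count of measured blood pressure cannot show the direction of a dose difference, and it weakens an excess in one direction: from 25 points to 22.5 or 20 under assumed equal background rises of 10% or 20%. The cases without a directional measured count are relative changes over 30% that stay within the absolute limits, with the baseline boundaries given in step 2. Those boundaries are arithmetic on the SAP's own limits. The event rates are assumptions, because the documents give none.

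The background figures of 33% to 71% should not carry weight on their own. They fall to about 5% at an SD of 5 mmHg, and splitting the row would reduce that background but not remove it, since much of it comes from comparing many readings with a single Day 1 value.

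This is a reporting gap of minor to moderate weight, worth closing because closing it is cheap. No view is taken on whether the SAP's 30% or the protocol's 25% is the right cut-off.

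**What to change.** In SAP 6.3 and Table 14.3.3.3, keep the SAP's 30% cut-off and replace the single row with four, each by dose group: systolic decrease, systolic increase, diastolic decrease and diastolic increase. The pooled row may stay as a total.

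Optionally, print the same four rows for infusion-day readings against that day's own pre-infusion value, the reference already used for Table 14.3.3.2. As planned, readings in the second dosing period (Days 85 to 89) are compared with a Day 1 value taken about 12 weeks before, and no count captures acute relative change within an infusion day.

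The cost is a wording change in the SAP and a few more rows in an existing table, with no new data. The downside is smaller counts per row.

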6.4 Electrocardiogram

P-R interval, QT interval, QRS duration, Ventricular heart rate and QTc intervals using Bazett's correction formula and Fridericia's correction formula will be investigated. QTc values will be used as reported, they will not be recalculated. Changes from baseline for all Electrocardiogram (ECG) parameters will be summarized at each scheduled timepoint (Days 5, 85, and 89) (Table 14.3.4.1). In addition, frequency tabulation of the overall ECG results (Normal, Abnormal NCS, and Abnormal CS) will be summarized (Table 14.3.4.2).

6.5 Physical Examinations

For physical examination data, when calculating the percentage reporting each category, the "Not Done" category will not be included in the denominator.

Number (%) of subjects with abnormal physical examinations will be tabulated at screening and Day 168 (Tables 14.3.5.1). Normal/abnormal shift from screening to Day 168 will also be provided (Tables 14.3.5.2).

6.6 C-SSRS since Last Visit

The frequency of individual C-SSRS since last visit assessments (Yes/No) will be summarized at each scheduled timepoint (Days 6 and 90) (Tables 14.3.6).

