4.2.2 SECONDARY ENDPOINTS

This study is neither designed nor powered to detect statistically significant differences in cognitive or motor domains between the Baseline and End of Study values. However secondary cognitive endpoints will be summarized over the study period from Baseline values using descriptive statistics:

- Changes in scores on the Mini-Mental State Examination (MMSE) ([Folstein 1975](#)) ([Appendix 1](#)).
- Changes in scores on the 11-item Alzheimer's Disease Assessment Scale-Cognitive Subscale (ADAS-Cog/11) ([Rosen 1984](#)) ([Appendix 2](#)).
- Changes in scores on the Grooved Pegboard Test ([Lafayette 2002](#)).
- Changes in scores on the Category Fluency Test (CFT) ([Acevedo 2000](#)).
- Changes in the Clinical Dementia Rating Scale – Sum of Boxes (CDR-SOB) ([Hughes 1982](#)) ([Appendix 3](#)).
- Changes in the Alzheimer's Disease Cooperative Study – Activities of Daily Living₂₃ (ADCS-ADL₂₃) ([Galasko 1997](#)) ([Appendix 4](#)).
- Changes on the Alzheimer's Disease Cooperative Study – Clinical Global Impression of Change (ADCS-CGIC) ([Ferris 1997](#)) ([Appendix 5](#)).

- Change on the Neuropsychiatric Inventory Questionnaire (NPI-Q) ([Kaufert 2000](#)) ([Appendix 6](#)).
- Change on the Savonix Neurocognitive Assessments and Digit Span ([Appendix 7](#)).

Secondary safety endpoints include:

- Changes from baseline in clinical laboratory parameters.
- Changes from baseline in vital sign measurements.
- Changes from baseline in the Columbia-Suicide Severity Rating Scale (C-SSRS) ([Posner 2011](#)) ([Appendix 8](#)).
- Changes on MRI scans designed to assess for ARIA.

Secondary feasibility endpoints include:

- Subject compliance with the study visit schedule, procedures, and infusions, and any required adaptations that are necessary for the study completion.
- Success of blinding. This will be assessed based on all occurrences (intentional or unintentional) of unblinding of blinded study subjects, their trial partners or study personnel (e.g. investigators, medical providers, cognitive testing raters, the Sponsor or their representatives).

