7.1.1.1.1 Columbia-Suicide Severity Rating Scale

The C-SSRS is a simple series of questions for the assessment of suicidal ideation and behavior in clinical trials ([Posner 2011](#)) ([Appendix 8](#)). The C-SSRS was designed to distinguish the domains of suicidal ideation and suicidal behavior in subjects who have expressed wishes to be dead or suicidal thoughts. Four constructs are measured. The first is the severity of ideation, which is rated on a 5-point ordinal scale in which 1=wish to be dead, 2=nonspecific active suicidal thoughts, 3=suicidal thoughts with methods, 4=suicidal intent, and 5=suicidal intent with plan. The second is the intensity of ideation subscale, which comprises 5 items, each rated on a 5-point ordinal scale: frequency, duration, controllability, deterrents, and reason for ideation. The third is the behavior subscale, which is rated on a nominal scale that includes actual, aborted, and interrupted attempts; preparatory behavior; and non-suicidal self-injurious behavior. And the fourth is the lethality subscale, which assesses actual attempts; actual lethality is rated on a 6-point ordinal scale, and if actual lethality is zero, potential lethality of attempts is rated on a 3-point ordinal scale. The use of a standardized measure such as the C-SSRS comprehensively assesses suicidal behavior and ideation.

The C-SSRS will be administered by interview at screening to assess suicidal ideation and behavior over the course

of the subject's lifetime and in the past 6 months. The C-SSRS will be repeated on Visits 8 and 16 to assess suicidal ideation and behavior for the time period since the subject's last C-SSRS assessment.

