2 GENERAL ANALYSIS DEFINITIONS

All analysis dataset preparations and statistical analyses will be performed using SAS® version 9.4 or higher. No imputation will be performed for missing data unless stated otherwise. Listings for CSR Appendix 16.2 will include all the subject data points being collected or derived for analyses, and will be sorted by treatment group, site, and subject number.

[figure not shown]

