4.3.3 Baseline Assessment of Columbia-Suicide Severity Rating Scale (C-SSRS)

The C-SSRS is a simple series of questions for the assessment of suicidal ideation and behavior in clinical trials (Posner 2011). The C-SSRS (including Actual Attempts Lethality) in both Lifetime and Last 6 Months are evaluated at screening visit.

Descriptive statistics or frequency tabulation will be provided for following C-SSRS parameters (Table 14.1.4.2):

- Suicidal Ideation (Yes/No): Wish to be Dead, Non-Specific Active Suicidal Thoughts, Active Suicidal Ideation without Intent to Act, Active Ideation with Some Intent without Specific Plan, Active Ideation with Specific Plan and Intent

- Intensity of Ideation
 - Most Severe Suicidal Ideation (1-5)
 - Frequency of Suicidal Ideation (1-5)
 - Duration of Suicidal Ideation (1-5)
 - Deterrents of Suicidal Ideation (0-5)
 - Controllability of Suicidal Ideation (0-5)
 - Reason of Suicidal Ideation (0-5)
- Suicidal Behavior:
 - Actual Attempt (Yes/No)
 - Total Number of Attempts
 - Interrupted Attempt (Yes/No)
 - Total Number of Interrupted Attempts
 - Aborted Attempt (Yes/No)
 - Total Number of Aborted Attempts
 - Preparatory Acts or Behavior (Yes/No)
 - Suicidal Behavior (Yes/No)
- Lethality - Most recent attempt:
 - Actual Lethality/Medical Damage (0-5)
 - Potential Lethality (0-2)
- Lethality - Most lethal attempt:
 - Actual Lethality/Medical Damage (0-5)
 - Potential Lethality (0-2)
- Lethality - Initial/First attempt:
 - Actual Lethality/Medical Damage (0-5)
 - Potential Lethality (0-2)

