Table 14.3.1.7.1	Incidence of Treatment-Emergent Adverse Events (TEAEs) for Preferred Terms Associated with Blood Pressure Changes by MedDRA System Organ Class and Preferred Term	SAF
Table 14.3.1.7.2	Incidence of Treatment-Emergent Adverse Events (TEAEs) for Preferred Terms Associated with Blood Pressure Changes by MedDRA System Organ Class and Preferred Term in Period 1	SAF
Table 14.3.1.7.3	Incidence of Treatment-Emergent Adverse Events (TEAEs) for Preferred Terms Associated with Blood Pressure Changes by MedDRA System	SAF

Number	Title	Population
	Organ Class and Preferred Term in Period 2	
Table 14.3.2.1.1	Changes in hematology measurements	SAF
Table 14.3.2.1.2	Changes in serum chemistry measurements	SAF
Table 14.3.2.1.3	Changes in urinalysis measurements	SAF
Table 14.3.2.2	Frequency of categorical laboratory assessments	SAF
Table 14.3.2.3.1	Shift Table in hematology measurements	SAF
Table 14.3.2.3.2	Shift Table in serum chemistry measurements	SAF
Table 14.3.2.3.3	Shift Table in urinalysis measurements	SAF
Table 14.3.3.1	Changes from baseline in vital sign measurements and weight	SAF
Table 14.3.3.2	Changes from pre-dose in vital sign measurements within each infusion day	SAF
Table 14.3.3.3	Blood pressure measurements of special interest	SAF
Table 14.3.4.1	Changes from baseline in ECG measurements	SAF
Table 14.3.4.2	Frequency of overall ECG results	SAF
Table 14.3.5.1	Frequency of abnormal physical examination results	SAF
Table 14.3.5.2	Shift Table in physical examination results	SAF
Table 14.3.6	Frequency of Columbia-Suicide Severity Rating Scale (C-SSRS) Since Last Visit	SAF

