11 LISTINGS FOR CSR APPENDIX 16.2

Number	Title	Population
Listing 16.2.1.1	Analysis Populations	SCRN
Listing 16.2.1.2	Screen Failures	SCRF
Listing 16.2.1.3	Subject Disposition	ITT
Listing 16.2.1.4	Protocol Deviations	ITT
Listing 16.2.1.5	Informed Consent	ITT
Listing 16.2.1.6	Study Visits	ITT
Listing 16.2.2.1	Inclusion Criterion Not Met or Exclusion Criteria Met	ITT
Listing 16.2.2.2	Assessment for AD using NIA-AA criteria	ITT
Listing 16.2.2.3	Drug Testing/Serology Screen	ITT
Listing 16.2.2.4	Randomization	ITT
Listing 16.2.3.1	Demographics	ITT
Listing 16.2.3.2	Baseline Characteristics	ITT
Listing 16.2.3.3	Baseline Assessment of Modified Hachinski Ischemia Scale (MHIS)	ITT
Listing 16.2.3.4.1	Columbia-Suicide Severity Rating Scale (C-SSRS) Lifetime	ITT
Listing 16.2.3.4.2	Columbia-Suicide Severity Rating Scale (C-SSRS) Last 6 Months	ITT
Listing 16.2.3.5	APOE Genotype	ITT
Listing 16.2.4.1.1	Medical History	SAF
Listing 16.2.4.1.2	Alzheimer's Disease History	SAF
Listing 16.2.4.2	Family Medical History	SAF
Listing 16.2.4.3	Social History	SAF
Listing 16.2.4.4	Exercise/Activity Level	SAF
Listing 16.2.4.5	Tobacco Use	SAF
Listing 16.2.4.6	Alcohol and Illicit Substance Use	SAF
Listing 16.2.4.7	PET Scan	SAF
Listing 16.2.4.8	Echocardiogram Results	SAF
Listing 16.2.5.1.1	Prior Medications	SAF
Listing 16.2.5.1.2	Previous Treatment for Alzheimer's Disease	SAF
Listing 16.2.5.2	Concomitant Medications	SAF
Listing 16.2.5.3	Extent of Exposure	SAF
Listing 16.2.5.4	Infusion Rate	SAF
Listing 16.2.5.5	Daily Summary of Infusion Administration	SAF
Listing 16.2.5.6	Treatment Completion	SAF
Listing 16.2.5.7	Tolerability	SAF
Listing 16.2.5.8	Assessment of Blinding	SAF
Listing 16.2.6.1	Mini-Mental State Examination (MMSE)	ITT
Listing 16.2.6.2	Alzheimer's Disease Assessment Scale-Cognitive Subscale (ADAS Cog/11)	ITT

Number	Title	Population
Listing 16.2.6.3	Grooved Pegboard Test (GPT)	ITT
Listing 16.2.6.4	Category Fluency Test (CFT)	ITT
Listing 16.2.6.5	Clinical Dementia Rating Scale – Sum of Boxes (CDR-SOB)	ITT
Listing 16.2.6.6	Alzheimer’s Disease Cooperative Study – Activities of Daily Living 23 (ADCS-ADL23)	ITT
Listing 16.2.6.7	Alzheimer’s Disease Cooperative Study – Clinical Global Impression of Change rating (ADCS-CGIC)	ITT
Listing 16.2.6.8	Neuropsychiatric Inventory Questionnaire (NPI-Q)	ITT
Listing 16.2.7.1	Non Treatment Emergent Adverse Events	SAF
Listing 16.2.7.2	Treatment Emergent Adverse Events	SAF
Listing 16.2.8.1	Clinical Laboratory Results	SAF

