Listing 16.2.8.2	ECG Results	SAF
Listing 16.2.8.3	MRI Testing	SAF
Listing 16.2.9	Vital Signs	SAF
Listing 16.2.10	Physical Examinations	SAF
Listing 16.2.11	Columbia-Suicide Severity Rating Scale (C-SSRS) Since Last Assessment	SAF

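### The protocol names change from baseline in C-SSRS as a secondary safety endpoint, but no SAP table links a subject's follow-up C-SSRS to baseline by dose

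*SAP*

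**What the plan says.** Protocol Section 4.2.2 includes among the secondary safety endpoints "Changes from baseline in the Columbia-Suicide Severity Rating Scale (C-SSRS"). The Protocol Summary repeats it.

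The baseline comes from screening. SAP Section 4.3.3 says: "The C-SSRS (including Actual Attempts Lethality) in both Lifetime and Last 6 Months are evaluated at screening visit". The results go into Table 14.1.4.2, with ideation items, intensity ratings, behaviour and lethality.

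For follow-up, Protocol Section 7.1.1.1.1 says: "The C-SSRS will be repeated on Visits 8 and 16 to assess suicidal ideation and behavior for the time period since" the previous C-SSRS. These visits are Days 6 and 90. SAP Section 6.6 gives the whole analysis in one sentence: "The frequency of individual C-SSRS since last visit assessments (Yes/No) will be summarized at each scheduled timepoint (Days 6 and 90"). The SAP's list of tables (Section 10) has one matching entry, Table 14.3.6: "Frequency of Columbia-Suicide Severity Rating Scale (C-SSRS) Since Last Visit".

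The SAP also plans subject-level listings (Section 11). Listing 16.2.3.4.1 covers Lifetime, Listing 16.2.3.4.2 is "Columbia-Suicide Severity Rating Scale (C-SSRS) Last 6 Months", and Listing 16.2.11 is "Columbia-Suicide Severity Rating Scale (C-SSRS) Since Last Assessment". SAP Section 2 says of these: "Listings for CSR Appendix 16.2 will include all the subject data points being collected or derived for analyses"; they are sorted by treatment group, site and subject.

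**The concern.** A declared change-from-baseline endpoint should have a summary in which each subject's later result is read against his or her own starting point. Here there are two separate sets of counts. A Yes at Day 6 or Day 90 is counted the same way whether the ideation is new, worse than at screening, or unchanged.

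Eligibility does not remove the problem. Protocol Section 5.2 excludes active ideation with at least some intent in the past 6 months, which corresponds to ideation items 4 and 5. A subject with a wish to be dead, non-specific thoughts, or thoughts of a method without intent (items 1 to 3) can enter.

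At stake is the by-dose reading of suicidality, where the useful figure is how many subjects in each dose group became positive or moved to a higher category. The planned tables do not give it.

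**Working it through.** No stated figure has to be reproduced. The check is a comparison of texts, a short identification argument, and the recall windows.

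**1. Is there a baseline-linked C-SSRS summary anywhere?**

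| Data | Baseline-linked summary in the SAP |
|---|---|
| Laboratory (6.2) | Change from baseline and shift tables |
| Vital signs (6.3) | Change from baseline |
| ECG (6.4) | Change from baseline |
| Physical examination (6.5) | Shift from screening to Day 168 |
| C-SSRS (4.3.3, 6.6) | None: counts at screening, counts at Days 6 and 90 |

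ECG and physical examination are not on the protocol's list of secondary safety endpoints, yet they get a baseline-linked summary. SAP Section 2.6 does not fill the gap: it sets the content of tables that summarize change, and Table 14.3.6 is a frequency table. SAP Section 8 explains departures for the Per Protocol set and for blood pressure, and is silent on C-SSRS.

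**2. What can two separate counts show?**

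Let *n* be the subjects in a dose group, *b* the number with Yes on an item at baseline, and *f* the number with Yes at follow-up, with the same *n* subjects assessed both times. The number newly positive lies between max(0, *f* − *b*) and min(*f*, *n* − *b*). Take *n* = 20, the planned group size. The values of *b* and *f* are assumed; the documents give none.

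| *b* | *f* | Lower | Upper | New cases |
|---|---|---|---|---|
| 0 | 2 | 2 − 0 = 2 | min(2, 20) = 2 | exactly 2 |
| 1 | 3 | 3 − 1 = 2 | min(3, 19) = 3 | 2 to 3 |
| 2 | 2 | 0 | min(2, 18) = 2 | 0 to 2 (0% to 10%) |
| 4 | 4 | 0 | min(4, 16) = 4 | 0 to 4 (0% to 20%) |

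With *b* = 0 the counts settle the matter. With any baseline positives, and enough negatives to take their place, they do not.

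**3. Which positives are ambiguous?**

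- Items 4 and 5: excluded at entry for the past 6 months, so a later Yes is new against that window unless there was an eligibility deviation.
- Behaviour: the follow-up form covers only the time since the previous assessment, so a reported act falls after screening.
- Items 1 to 3: may be present at entry. The ambiguity lies mainly here.

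**4. What do the recall windows cover?**

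Screening is at Day −28 to −8. SAP Section 2.3 defines no Day 0, so screening is 28 to 8 days before the first infusion, and Day 6 is 5 days after it.

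- Day 6 window: 28 + 5 = 33 days at the longest, 8 + 5 = 13 at the shortest. The pre-dose share is 28/33 = 85% to 8/13 = 62%.
- Day 90 window: 90 − 6 = 84 days, wholly after the first infusion provided the Day 6 assessment was done. The ±7-day allowance at Visit 11 makes it 77 to 91 days.
- Baseline window: 6 months or lifetime. SAP Section 2.3 makes the last pre-dose assessment the baseline, which fixes the visit but not which of these two recall periods applies.

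So most of the Day 6 window precedes any dose, and both follow-up windows are shorter than the 6-month baseline.

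**The case against.** The strongest reply is that nothing is lost. The listings hold every subject's screening and follow-up answers, sorted by dose group. With about 40 subjects and few events expected, a reader can trace each positive case by hand. This stands, and it rules out a stronger conclusion that a reader might draw: that new or worsened suicidality cannot be told from persisting ideation at all. It can, from Listings 16.2.3.4.2 and 16.2.11, and the entry exclusion and the follow-up form settle most questions about items 4 and 5 and about behaviour. But a listing is not a summary by dose, and without a named baseline window two readers could count differently.

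Second, clinically significant findings that are new or worse can be reported as adverse events (Protocol Section 8.1.1) and so reach the by-dose TEAE tables (SAP Sections 6.1.2 and 6.1.5). This also stands in part. It depends on the investigator's judgement, and AD symptoms in line with the subject's usual course are not adverse events unless serious.

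Third, Protocol Section 10.4.1 prescribes counts and percentages for categorical endpoints, and Section 10.4.4 names change from baseline for laboratory tests and vital signs only. It is right that no protocol text demands a C-SSRS shift table, so the SAP breaks no explicit instruction on method. The endpoint is still worded as a change, and the separate tables do not show one.

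Finally, a simple shift table could mislead. A reader might take every higher category at Day 6 as treatment-emergent; the recall window does not support that. This objection shapes the fix but does not remove the need for it.

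**Conclusion.** The point holds in a limited form. The declared C-SSRS change endpoint has no by-dose summary that links follow-up to baseline, and the SAP does not declare the omission. The consequence is confined mainly to ideation items 1 to 3. New or worsened cases there must be found in the listings, or in adverse event reports where the investigator has judged them clinically significant.

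The importance is minor. The illustration of 0 to 2 new cases in 20 rests on assumed counts and complete follow-up. If no subject is positive at screening, Table 14.3.6 already gives the number of new cases. What is affected is the reading of a few individual cases; no test or sample size depends on it.

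**What to change.** In SAP Section 6.6:

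- Name the screening Last 6 Months assessment as the C-SSRS baseline.
- Add one shift table by dose on the Safety Set: worst ideation category (none, 1 to 5) at baseline against Day 6 and against Day 90.
- Below it, give the number (%) of subjects in a higher category than at baseline and the number with any suicidal behaviour since the last assessment.
- Label a higher Day 6 category *new or worse since screening*. Call it treatment-emergent only if onset is after the first infusion. The Day 90 window raises no such problem when the Day 6 assessment was done.
- Footnote that the 6-month baseline window is longer than the follow-up windows, so the shift leans towards apparent improvement.

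If the table is not wanted, declare the departure in SAP Section 8. The cost is a few lines of SAP text and one small table from data already collected. The one small downside is the lean from unequal windows, which the footnote discloses but does not remove.
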